2.5 Inclusion and Exclusion Criteria

2.5.1 Participants will be eligible for this study if they:

- Are 18 – 65 years old
- A score of 10 or higher on the Insomnia Severity Index*
- Are admitted as a treatment-seeking inpatient on 1SE under protocol 14-AA-0181 (signing both the clinical and research consent)
- Have been inpatient for at least 14 days prior to consent/screening
- Can speak, understand, and write in English
- Are able to comply with study requirements (including ability to access the Internet at least 2x per week)

2.5.2 Participants will be ineligible for this study if they:

- Are pregnant
- Are a prisoner
- Report a physician diagnosis of moderate to severe obstructive sleep apnea (OSA) OR test positive for moderate to severe OSA as documented with an Apnea Hypopnea Index of 15 events/hour based on WatchPAT testing results
- Have irregular sleep schedules that prevent the ability to follow treatment recommendations (i.e. usual bedtimes outside of 8:00 pm to 2:00 am or arising times outside of 4:00 am to 10:00 am)
- Meet SCID-5/DSM-5 criteria for opioid use disorder in the past year
- Meet SCID-5/DSM-5 criteria for severe cocaine use disorder and/or severe cannabis use disorder in the past year
- Meet diagnostic criteria for an unstable or serious psychiatric condition (schizophrenia, bipolar, major depressive disorder not currently in remission) - based on diagnosis from the SCID for DSM-5
- Are participating in any experimental pharmacological intervention study
- Presence of unstable or serious medical/neurologic illness at PI and MAI discretion

2.5.3 Justification for certain inclusion/exclusion criteria

*Morin, Belleville, Bélanger, and Ivers (2011) recommend an ISI cutoff score of at least 10 in detecting clinical insomnia while preserving very good specificity and sensitivity in a population-based or clinical trial sample.

One of SHUT-I's potential side effects from its sleep restriction phase is increased daytime sleepiness. Increased daytime sleepiness is associated with increased frequency of falls in the elderly (individuals >65 years old) (Helbig et al., 2013), thus we are excluding individuals over the age of 65.

Protocol Number: 18-CC-0079

Among individuals who are alcohol-dependent with untreated moderate-severe OSA, sleep restriction may further increase sympathetic and stress response, leading to an increased risk of cardiovascular adverse events (Irwin & Ziegler, 2005). Severe OSA is associated with increased daytime sleepiness, motor vehicle crashes, depression, cardiovascular and cerebral morbidity and mortality, cognitive and metabolic dysfunction (Peppard & Hagen, 2017). Thus, we are excluding individuals with untreated moderate-severe OSA.

A study by Pacek, Herrmann, Smith, and Vandrey (2017) reported that participants reported sleep difficulties with abstinence from cannabis and resulted in the relapse in cannabis use at a later time. It is unclear whether sleep difficulty symptoms improve with relapse, but the authors also point out that cannabis use contributes to observed sleep difficulties. Whether or not disordered sleep contributes to long-term cannabis use is unclear (Pacek, Herrmann, Smith, & Vandrey, 2017). Finally, cannabis is independently associated with impairment of sleep continuity (Pacek et al., 2017). Thus, we are excluding participants who meet the criteria SCID-5/DSM-5 criteria for severe cannabis use disorder.

Cocaine is a stimulant that can disrupt sleep and sleep architecture in both humans and animals (Angarita, Emadi, Hodges, & Morgan, 2016; Cortes et al., 2016; Irwin, Bjurstrom, & Olmstead, 2016). Increased arousal is the most common effect of cocaine use with regards to sleep and animal models showed that the level of arousal is dose dependent (Chakravorty, Vandrey, He, & Stein, 2018; Cortes et al., 2016). Individuals who are diagnosed with cocaine use disorder (CoUD) have an underlying sleep disturbance that may persist even after abstinence for several weeks, although recent evidence suggests that improving sleep may increase the likelihood of sustained abstinence from cocaine (Angarita et al., 2016; Hodges, Pittman, & Morgan, 2017; Winhusen, Theobald, & Lewis, 2019). CoUD as well as other substance use disorders are commonly comorbid with AUD (Chakravorty et al., 2018). For this study, we will only exclude participants who meet the DSM-5 criteria for severe CoUD. During analysis, we will attempt to control for any comorbid substance use disorders.

Opioids are associated with a more complex picture of sleep disorders that includes insomnia, obstructive sleep apnea, and complex sleep apnea (Hassamal, Miotto, Wang, & Saxon, 2016). Patients who are diagnosed with opioid use disorder are usually treated with oral naltrexone. "Oral naltrexone is capable of inducing fatigue, nausea, sleepiness, restlessness, and dysphoria in nonopiate users during the first few hours acutely post-ingestion" (Mysels, Cheng, Nunes, & Sullivan, 2011, p.22). Insomnia also transiently worsened with naltrexone treatment, but it is purported to be associated with subacute opiate withdrawal (Mysels et al., 2011). Thus, we are excluding participants who meet the SCID-5/DSM-5 criteria for opioid use disorder regardless of severity.

A previous study on predictors of dropout in a CBT-I program indicated a drop-out rate of around 34%. Based on potential dropout of those individuals who are eligible and are randomized in Phase II (conservative estimate: 40%), and a target of 20 individuals per group, we have adjusted our accrual ceiling to 67 (plus 12 for Phase I). We will submit an amendment to adjust this number if we discover the prevalence and severity of OSA in the population is higher than our estimate based on results from the WatchPAT screening.

Any experimental pharmacological agent may affect the data collected for this study and its effect on sleep will be largely unknown. As a result, our research team decided on excluding participants that are enrolled in any experimental pharmacological study.

PI Name: [name]

Version Date: 12/07/2020

Protocol Number: 18-CC-0079

Study measures have only been validated in English.

Additional note: after enrollment in the study, the management of sedatives/hypnotics for individuals who have been prescribed either will be done by a clinician who is blind to the treatment condition.

Protocol Number: 18-CC-0079

3 Statistical analysis:

Qualitative analysis (Phase I participants only). Each audio-recorded interview will be transcribed verbatim. A codebook will be developed based on themes from the interviews. Each code will be accompanied by an operational definition that will allow for clarity and consistency in the coding process. Evidence of each code or theme will be assessed using quotes from the interviews. A team of coders will independently review all transcripts. Discordant coding will be discussed until consensus among the coding team is achieved. Once the iterative process of consensus building is complete, an intramural expert in qualitative methodology will validate the final themes and coding. After data are coded, NVivo will be utilized for further qualitative analysis and data management.

Quantitative analyses (Phase II only). The first step in quantitative data analysis will be running baseline "diagnostics" to check for outliers and normal distribution of all continuous variables. If the assumptions of normality are not violated, we will proceed with parametric testing. If the assumptions of normality are violated, non-parametric tests will be utilized. For quantitative analyses, statistical significance will be considered at $p < 0.05$.

Descriptive data will include frequencies for categorical variables and range, mean, and standard deviation for continuous variables. Patterns of missing data will be examined thoroughly to assess whether any questions were systematically skipped by all participants or any sub-group of participants. Initial analyses will be descriptive and exploratory in nature to any changes in insomnia severity (as measured by the ISI) over time. Relationships between variables will be examined with bivariate correlation coefficients (for two continuous variables), Chi-squares (for two categorical variables), and t-tests or ANOVA (for one categorical and one continuous variable).

Actigraphy analyses. After device removal and data download, raw data from the *Actiwatch Spectrums* will be analyzed using the Philips Respironics computerized sleep scoring software, which scores each epoch based on a threshold method algorithm. Investigators will review each sleep period prior to analysis to screen for malfunctioning watches, corrupt data, and required adjustments using bedtimes and wake times from self-reported diary data when necessary.

Power analysis: In studies of CBT-I, the effect sizes for improvements in insomnia severity ranged from $d=0.2$ (Ritterband et al., 2016) to $d=2.24$ (Ritterband et al., 2012), with the sample sizes ranging from 29 (Ritterband et al., 2012) to 300 individuals (Ritterband et al., 2016). One such study also provided effect sizes for improvements in several other sleep-related variables, including wake after sleep onset ($d=0.74$), sleep onset latency ($d=0.26$), and sleep efficiency ($d=0.68$; b - Ritterband et al. 2009).

Phase I: 10 participants – the qualitative phase is not meant to infer, generalize, or generate statements about the population as a whole. Thus, our sample size is based on the concept of *saturation*, which describes the number of participants at which no new themes are being generated. It is expected that 12 patients will be screened to achieve 10 “completers” (i.e. individuals providing pre- and post-test assessment data).

Protocol Number: 18-CC-0079

Phase II: 60 participants - the total sample size for phase II of this study will test the primary hypotheses associated with the analysis plan. With insomnia severity as the primary outcome, we will use a two-sided alternative hypothesis that the rate of change will be different between the intervention group and the control group. Assuming a correlation of 0.6 between the two time points, an alpha level of 0.05, a power level of 0.8, and an estimated attrition rate of 40 percent, we will be able to detect an effect size of 0.84 with 60 participants (Fitzmaurice, Laird, & Ware, 2012). Permuted block randomization with block size of four will be used to equally assign participants in each group. The statistician, who will not have any contact with participants, will prepare the randomization sequences and give out the allocation assignment after each participant is consented.

Mixed model for repeated measure with group, time, and the interaction of group by time will be used to test the changes of insomnia severity in two groups. Mixed model for repeated measures will also be used to test the secondary objectives with potential covariates in the model. Demographic, psychiatric, and/or drinking-related factors significantly related to the outcomes listed in the secondary objectives will be entered in the model. Aikake information criterion and the Bayesian information criterion will be used to select best-fitting models. A potential dosing effect analysis including the number of cores completed as a covariate will be conducted for the treatment group only. With the linear mixed model approach, all available data points will be included in the analyses. Under missing completely at random and missing at random assumptions, linear mixed model with restricted maximum likelihood estimation can produce unbiased estimators (Salim, Mackinnon et al. 2008).

Investigator Conflicts: NIH guidelines on conflict of interest have been distributed to all investigators. NIH guidelines on conflict of interest have been distributed to all investigators.

Technology Transfer: No technology transfer agreement is in place for this protocol.

4 Rationale for subject selection

This study will be open to both males and females of all racial and ethnic groups, without targeting any specific group. We anticipate the target enrollment of participants to reflect the racial/ethnic distribution of residents in the greater Washington DC metropolitan area.

5 Recruitment plan

Following IRB approval, all eligible participants admitted to the Clinical Center alcohol rehabilitation unit (1SE) who sign the clinical and research consents for 14-AA-0181 will be approached for participation in this study. The PI or a designee will explain the study objectives, time commitment, expectations, and processes for assessments.

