1.1 Theoretical framework

This study will examine sleep-related beliefs and behaviors in the context of the Social Cognitive Theory (SCT; Bandura, 1986). Self-efficacy is perhaps the most well-established construct in the SCT and was an important predictor of sleep quality in our pilot work (Brooks et al., *Under Review*). We anticipate that the SHUTi program will directly impact personal, environmental, and behavioral factors for participants, and the theory includes all three as potential predictors of outcomes (insomnia severity and ultimately relapse).

1.2 Study Objectives:

1. *Phase I:* Assess the feasibility and acceptability of Internet-based CBT-I among individuals with AUD in recovery
2. *Phase II:* Compare the efficacy of CBT-I versus an education-only control group with respect to primary and secondary outcome variables
 - a. Primary outcome variables include: changes in insomnia severity over time, changes in actigraphy-recorded sleep efficiency over time
 - b. Secondary outcome variables include actigraphy-related (objective) variables, alcohol consumed (post-discharge), alcohol craving (post-discharge), sleep disturbance, daytime sleepiness, anxiety/depression, fatigue, self-efficacy for sleep, dysfunctional beliefs about sleep, and functional outcomes
 - c. Explore specific domains associated with improved outcomes: e.g. demographic, psychiatric, and/or drinking-related factors

2 Study design and methods

This is a two-phase study. Phase I will be focused on assessing feasibility and effectiveness of program delivery and data collection (n=10). Phase II will be a pilot RCT powered to examine intervention

Protocol Number: 18-CC-0079

effectiveness in the target population (n=20 per group). All study participants will receive a handheld tablet to access the SHUTi or education-only program.

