2.2 Phase II

Randomization will be achieved using a random number generator, assigning equal numbers of participants to each of the two conditions. The PI and AIs will remain blind to the randomization scheme until each study participant is deemed eligible and signs the consent form.

Intervention/control groups (Phase II only)**:

1. **Intervention group:** 6 sessions (“modules”) of SHUTi intervention (at least one module completed while inpatient, the rest while outpatient): In SHUTi, customization is based on multiple variables, including sleep diary responses. The SHUTi program tailors specific recommendations based on sleep diary responses or other input within the program (e.g., responses on the Dysfunctional Beliefs and Attitude Scale trigger recommendations for specific cognitive restructuring strategies).
2. **Control group:** education/monitor only (insomnia education web-based program that participants access and read at their own pace – contains no customization of program based on sleep diary responses). Participants in the control group are given educational information (like they might see on WebMD or National Sleep Foundation websites), but are left to apply it themselves.

**Participants who are randomly assigned to the intervention condition will be granted access to the program free of charge for up to six months from the start of the program. Participants who are randomly assigned to the education-only condition will be given access to the full SHUTi program three months after discharge upon request. Similarly, participants who are randomly assigned to the intervention condition will be granted access to the education materials provided to the education-only condition participants three months after discharge upon request.

All participants enrolled in this study will first be admitted under the screening and assessment protocol on the 1SE clinic (14-AA-0181), which includes adults at least 18 years of age seeking treatment for alcohol use disorders. Once consented and enrolled into the inpatient treatment, screening, and research protocol, participants are screened and recruited enrollment in additional studies for which they meet eligibility criteria (including the study described herein). Study participants will be asked to

Protocol Number: 18-CC-0079

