Objective measure of sleep: actigraphy. "Actiwatches" are small wristband data loggers that record digitally-integrated measures of gross motor activity. These devices contain accelerometers and light sensors in order to objectively assess sleep. Prior studies have demonstrated actigraphy's high sensitivity with moderate accuracy for detecting sleep in populations with normal and disturbed sleep when compared to polysomnography (Kushida et al., 2001; Paquet et al., 2007). The *Actiwatch Spectrum Plus* (Philips Respironics) has been used in previous studies with patients on 1SE in both inpatient and outpatient settings. The watch is worn on the non-dominant wrist. Study participants will be asked to wear an actiwatch for 4 days, 3 nights (Phase I only) and for at least 1 week (Phase II only) at three study time points (Pre SHUT-i®/Education-Only initiation, 3-4 weeks after SHUT-i®/Education-Only initiation and Post SHUT-i®/Education-Only program completion). Participants will return the actiwatches either in person (if the participant will be returning to the Clinical Center) or by mail after each study time point so that the research team can download the data and return the watch to the participant (with the exception of the last study time point). The main outcome of interest will be improvements in sleep efficiency from baseline to follow-up assessment periods. The watch also provides measures of total sleep time (TST), wake after sleep onset (WASO), sleep onset latency (SOL), number of awakenings (NWAK), and time in bed (TIB).

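### Actigraphy sleep periods behind a primary outcome are edited at investigators' discretion, with no stated edit criterion and no provision for masked review

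*Combined protocol and SAP*

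**What the plan says.** Section 1.2 lists the primary outcomes: "Primary outcome variables include: changes in insomnia severity over time, changes in actigraphy-recorded sleep efficiency over time". Section 2.4, on actigraphy, says of the watch data: "The main outcome of interest will be improvements in sleep efficiency from baseline to follow-up assessment periods".

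Section 3 (Actigraphy analyses) describes two steps. The first is automatic: the manufacturer's software, "which scores each epoch based on a threshold method algorithm". The second is manual: "Investigators will review each sleep period prior to analysis to screen for malfunctioning watches, corrupt data, and required adjustments using bedtimes and wake times", these times being taken "from self-reported diary data when necessary". The review covers every sleep period. The text does not say what makes an adjustment necessary or when a recording is rejected.

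On knowledge of the arm, Section 2.2 says: "The PI and AIs will remain blind to the randomization scheme until each study participant is deemed eligible and signs the consent form". In the Phase II sample-size paragraph of Section 3, the statistician is to prepare the sequence and "give out the allocation assignment after each participant is consented". The only role described as masked after enrollment is in the closing note of Section 2.5.3, where management of sedatives and hypnotics "will be done by a clinician who is blind to the treatment condition". No section describes a masked actigraphy reader, files without arm labels, a written editing rule or a second reader.

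**The concern.** Of the two primary outcomes, insomnia severity is self-reported and actigraphy is the one the protocol presents as objective. An objective measure is useful here because participants can hardly be kept unaware of whether they received the interactive program or the reading material. Part of that advantage is lost if the person who decides whether to move a sleep interval, or discard a recording, may know the arm and has no rule to follow.

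The interval matters because sleep efficiency, as usually defined, is sleep time divided by time in bed. Moving a boundary changes the denominator even though no epoch is rescored. A reviewer who knows the arm may also hold an expectation: the intervention includes sleep restriction (Section 1), and Section 2.4 uses the experimental group's diaries to check adherence to a prescribed sleep window. The same diaries are the source for the interval edits. If edits differed systematically by arm at follow-up, the difference would enter the treatment comparison as if it were an effect.

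**Working it through.** **1. Can the reviewers know the arm?** Section 3 names investigators as reviewers. Section 2.2 states blindness for the principal and associate investigators only up to eligibility and consent. Section 3 has assignments given out after consent. Section 10 lets study staff see responses inside the program. Nothing restores masking before the files are read. So the plan allows a reviewer to know the arm; it does not say that the reviewer does.

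**2. Sample size and precision.** The plan gives 60 participants, 40% attrition, correlation 0.6, two-sided alpha 0.05, power 0.80 and a detectable effect of 0.84 (Section 3, Phase II).
- Completers: 60 × 0.6 = 36, or 18 per arm.
- SD of change, in units of the single-occasion SD: √(2 × (1 − 0.6)) = 0.894.
- Standard error of the difference in mean change: 0.894 × √(2/18) = 0.298.
- Detectable effect: (1.96 + 0.842) × 0.298 = 0.835, which agrees with the stated 0.84.

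That calculation is for insomnia severity. Applying its correlation and completer numbers to sleep efficiency is an assumption.

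**3. What a boundary shift could do.** The documents give no mean or SD for sleep efficiency. Assumed: 480 min in bed, 384 min asleep (384/480 = 80%), SD 8 to 12 points, no true effect. All trimmed minutes are taken as scored wake, and the trim is a net average over all follow-up nights in one arm only, with none at baseline.
- Efficiency after trimming m minutes = 384/(480 − m).
- d = shift/SD, and θ = d/0.298.
- False-positive rate = 1 − Φ(1.96 − θ) + Φ(−1.96 − θ).

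| Average trim | Efficiency | Shift (points) | d at SD 12 to 8 | False-positive rate |
|---|---|---|---|---|
| 5 min | 384/475 = 80.84% | 0.84 | 0.07 to 0.11 | 5.6% to 6.4% |
| 10 min | 384/470 = 81.70% | 1.70 | 0.14 to 0.21 | 7.6% to 11.0% |
| 15 min | 384/465 = 82.58% | 2.58 | 0.22 to 0.32 | 11.1% to 19.1% |

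Example, 15 min at SD 8: d = 2.58/8 = 0.323; θ = 0.323/0.298 = 1.08; rate = 19.1%.

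For scale, Section 3 cites an effect of d = 0.68 on sleep efficiency from one study. A 15-minute shift would be 0.22/0.68 = 0.32 to 0.32/0.68 = 0.47 of that.

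**4. Lower end.** If the trimmed minutes hold sleep in the same proportion as the rest of the night, nothing changes: 15 min removes 12 min of sleep, and (384 − 12)/(480 − 15) = 372/465 = 80%. Edits that are equally frequent in both arms also cancel on average. The range therefore starts at zero.

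**The case against.** The best reply is that the plan is silent on masking at scoring and does not describe open scoring. Section 2.2 speaks of the randomization scheme. Read with the statistician's role in Section 3, it is mainly a statement about allocation concealment. A reader might infer from it that the scorers are known to be unmasked. The documents do not say so: they do not identify which investigators review the files or what labels those files carry. This part of the objection stands, and knowledge of the arm has to be called an inference.

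A reader might also infer that manual review removes the objectivity of actigraphy. That goes too far. Epochs are scored by algorithm, edits draw on the participant's own diary times, and they are made only when thought necessary. Discretion is limited to boundaries and exclusions, so protection is weakened but not removed.

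Three further points have force. The larger shifts in the table are worst cases, and at least a week of recording per time point in Phase II dilutes occasional edits. Sections 6.1 and 10 already provide for coded data with the key held apart, although a participant code does not by itself hide the arm. The masked clinician for sedatives guards against unequal co-treatment, so it does not show how actigraphy was meant to be read.

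What the objection does not answer is that a discretionary edit to the denominator of a listed primary outcome has no criterion, and that nothing keeps the arm from the person making it.

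**Conclusion.** The point holds as a weakness in the scoring procedure, and the sponsor should correct it. Reviewers may know the arm, they may move boundaries or reject data, and no rule binds them.

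The size cannot be fixed from the documents. Under the assumptions set out above, an average one-arm shift of 5 minutes is about 0.1 SD and nearly negligible, and 15 minutes is about 0.2 to 0.3 SD. These figures show what a systematic difference would do. They do not show that one will occur, and a reader should not take 11% to 19% as the trial's expected false-positive rate.

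The reach is limited to the actigraphy outcome. Insomnia severity, which the sample-size paragraph and the main model sentence in Section 3 address, is untouched, and the sample size need not change.

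**What to change.** In Section 3 (Actigraphy analyses):

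1. Set one written rule, the same for both arms, for when diary times replace the software interval and when a night is excluded.
2. Have files reviewed under a study code without arm labels, with diary bed and wake times supplied as plain values. The code should be one the reviewer cannot link to a participant whose arm he or she knows. Visit labels need not be removed.
3. Lock all edits and exclusions before arm labels are merged.
4. Report unedited, software-scored sleep efficiency as a sensitivity analysis.

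The cost is a little data-handling time; participant procedures do not change. Masking may be imperfect, because sleep restriction can show in the recordings and in the diary times. The fixed rule and the unedited analysis therefore carry most of the protection.

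### A fixed block size of four, printed in the protocol, lets anyone tracking past allocations know on average one third of upcoming Phase II assignments with certainty

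*Combined protocol and SAP*

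**What the plan says.** The Phase II paragraph of Section 3 (Statistical analysis) gives the method: "Permuted block randomization with block size of four will be used to equally assign participants in each group". It mentions no varying block sizes, no stratification and no withholding of the block size. Section 2.2 describes a random number generator "assigning equal numbers of participants to each of the two conditions", so each block holds two assignments to each arm.

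A statistician without participant contact prepares the sequence and is to "give out the allocation assignment after each participant is consented". On what investigators know, Section 2.2 says: "The PI and AIs will remain blind to the randomization scheme until each study participant is deemed eligible and signs the consent form". The only blinding stated for the period after enrolment (end of Section 2.5.3) is for the clinician who manages sedatives and hypnotics.

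Recruitment is from the 1SE unit alone. Under Section 5, the PI or a designee approaches eligible patients and explains the study. Most criteria in Section 2.5 are measured, but one inclusion criterion is ability to comply with study requirements, and the last exclusion reads "Presence of unstable or serious medical/neurologic illness at PI and MAI discretion". The text after Figure 1 in Section 2.4 places consent, apnea screening (after consent) and randomization in days 14 to 21 of the inpatient stay.

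**The concern.** Concealment has two parts: nobody should be told the next assignment, and nobody should be able to work it out. Release by an independent statistician secures the first. The second fails when allocation is from a single sequence, earlier assignments are known, and the block size is fixed and printed in the working protocol. Once two participants in a block have gone to the same arm, the remaining two must go to the other, and the fourth place in every block is always known.

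The group that appears to learn earlier allocations also approaches patients and makes the judged eligibility decisions. A view about who suits the active program could therefore, even without intent, affect who is enrolled when the next assignment is known. Insomnia severity, one of the two primary outcomes, is self-reported and may depend on traits such as motivation that staff can perceive. At stake is the comparability of the arms, not the precision of the estimate.

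**Working it through.** **Inputs.** Block size 4, ratio 1:1, 60 participants, correlation 0.6, two-sided alpha 0.05, power 0.80, attrition 40% and detectable effect 0.84 (Sections 2.2 and 3); accrual ceiling 67 for Phase II (Section 2.5.3).

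**The plan's own figure.** In units of the outcome SD, the change from baseline has variance 2 × (1 − 0.6) = 0.8. The number per arm is 2 × (1.960 + 0.842)² × 0.8 / 0.84² = 17.8, rounded up to 18. Then 36 / (1 − 0.40) = 60, which matches. The 0.84 is therefore a difference between arms in change, expressed in SDs of the outcome.

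**Assignments known with certainty.** A 2 + 2 block has six equally likely orders:

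- AABB and BBAA: positions 3 and 4 are determined (2 × 2 = 4).
- ABAB, ABBA, BAAB and BABA: position 4 only (4 × 1 = 4).

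That is 8 of 24 positions, or 33.3%. Sixty participants make 15 blocks, so the expected number is 15 × 8/6 = 20. The minimum is 15 (one per block) and the maximum 30 (two per block). At 67, there are 16 full blocks plus three places: 16 × 8/6 + 1/3 = 21.7.

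**Best guess.** Guessing the arm with more places left, and tossing a coin when they are level, is right with probability 1/2, 2/3, 2/3 and 1 at positions 1 to 4. The average is 17/24 = 70.8%, against 50% with unpredictable allocation.

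**With block sizes 4 and 6 in random order.** Assume the two sizes are equally likely, and take an observer who knows both possible sizes but not the size of any given block. Over 60 assignments, certain knowledge falls to about 5.6% (60 × 0.056 = about 3.4 assignments). Best-guess accuracy falls to about 69.1%.

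**What this could do to the comparison.** Suppose that at every guess the enrolled patient's prognosis for change in ISI is shifted by +s or −s SD according to the guessed arm. With guess accuracy p, the expected difference between arms without any treatment effect is 2 × s × (2p − 1). The values of s are assumptions; the documents give none.

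| Assumed s (SD) | Fixed 4, p = 0.708 | Random 4/6, p = 0.691 |
|---|---|---|
| 0.10 | 0.08 | 0.08 |
| 0.25 | 0.21 | 0.19 |
| 0.50 | 0.42 | 0.38 |

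If the shift were in baseline ISI alone, only part would reach the group-by-time test. With correlation 0.6 and equal variances, a baseline difference of 0.21 SD gives a difference in change of (1 − 0.6) × 0.21 = 0.08 SD.

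**The case against.** The case for leaving the plan as it is has substance. An independent statistician releases each assignment only after consent. Section 5 has all eligible patients approached, which limits choice over whom to enroll. Most criteria are measured: ISI score, apnea index, diagnostic interview, age, and bed and rise times. Apnea screening falls between consent and randomization, so staff obtaining consent do not yet know whether that patient will be randomized or, where candidates overlap, which place in the block the patient will take. Actigraphy-recorded sleep efficiency, the other primary outcome, is not self-reported. This is a small pilot, and a fixed block is a recognized choice.

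All of that stands, and it narrows the route to bias. It does not close it: two criteria rest on judgement, the order of randomizing patients within days 14 to 21 is not fixed, and none of these safeguards stops the counting.

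A reader might infer from the table that the trial faces a bias of 0.21 SD, a quarter of the detectable 0.84 (0.21/0.84 = 0.25). The documents do not support that. The figure rests on one assumed shift, acted on at every guess, and the ratio holds only if selection acts on prognosis for change; through baseline ISI alone the corresponding figure is 0.08. It also derives from best-guess accuracy, which varying the blocks hardly alters, so it cannot be presented as harm that the change removes.

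**Conclusion.** The point holds as a weakness in concealment that is cheap to reduce. On average one third of Phase II assignments, about 20 of 60, can be known in advance with certainty by anyone who knows the earlier allocations and the printed block size. The enumeration is exact; the realized share can run from 25% to 50%.

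The conclusion depends on investigators learning past allocations. The protocol does not state this outright; it follows from blinding that ends at consent and from the absence of any later blinding of the PI and AIs. If the blinding in Section 2.2 was meant to cover the block size, printing the size in Section 3 defeats it.

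It would go too far to conclude that selection bias has occurred, or that concealment is the trial's only protection against it. The documents show a route, partly guarded, and no evidence on its use. The size of any bias is unknown, and the planned sample size of 60 is not called into question.

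**What to change.** Have the statistician generate the Phase II list with randomly varying block sizes, for example 4 and 6 in random order. Replace the sentence in Section 3 with one saying that permuted blocks of varying, undisclosed size will be used, and keep the sizes in a restricted randomization file. If Phase II is under way, apply this from the next unused block.

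The gain is in certain knowledge, from 33.3% to about 5.6% even for an observer who knows the possible sizes. Best-guess accuracy stays near 69% for that observer, which is why the sizes should also be withheld. Recording the final eligibility decision before each assignment is released would support this at little cost.

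The cost is a regenerated list, an amended sentence, and a possible final imbalance of up to three participants. At a total of about 60, a difference of three costs (3/60)² = 0.25% of the information, so power is essentially unchanged.
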